**Table 6. Doses Planned Based on Participation from C5351004**

Participants from Part	Planned Dose to Initiate Treatment in Open Label Extension	Dose Adjustment
A	150 mg osivelotor	If dose is increased, a loading dose may be required. Details on the loading doses are provided in Section 11.3. The maintenance dose for all participants who have already enrolled in C5351005 prior to this amendment may be modified to 150 mg.
B	Adults: Initiate or continue with QD osivelotor 150 mg dose from Part B of C5351004. Adolescents: Initiate or continue with QD dose of osivelotor from Part B of C5351004.	Adults: Not applicable  Adolescents: Adolescent participants will be administered a dose that provides generally equivalent exposure to adult participants.
C	Continue with QD assigned dose of osivelotor from Part C of C5351004.	Treatment may be modified based on emerging data from C5351004. Adolescent and pediatric participants will be administered a dose that provides generally equivalent exposure to adult participants.

Abbreviations: QD, once daily.

Detailed information on loading dose and maintenance dose to be used based on prior participation in C5351004 can be found in Section 11.3.

#### 5.4. End of Study Definition

The EOS is defined as the date when the last participant has completed all study procedures up to and including EOS or ET visits, as specified in the Schedules of Assessments and Procedures (Section 2.1).

## 6. STUDY POPULATION

Prospective approval of protocol deviations to recruitment and enrollment criteria, also known as protocol waivers or exemptions, is not permitted.

### 6.1. Inclusion Criteria

Participants must meet all inclusion criteria to be eligible for study participation.

1. Aged 6 months or older with SCD who participated and received study drug in an osivelotor clinical study and completed the EOT visit.

Note: Participants who discontinued study drug in the originating study due to an AE, but who remained on study, may be eligible for treatment in this study provided the AE does not pose a risk for treatment with osivelotor. Also, participants who completed treatment from the originating study but were not able to rollover into C5351005 due to delay in study site activation will be eligible provided other eligibility criteria are met.

2. Females of child-bearing potential are required to have a negative urine pregnancy test prior to dosing on Day 1.

Note: Females who become of child-bearing potential during the study must be willing to have a negative urine pregnancy test to remain in the study.

3. If sexually active, females of child-bearing potential must consistently use highly effective methods of contraception consistently throughout the study and for at least 84 days after the last dose of study drug. Male participants are eligible to participate if they agree to the following requirements during the study intervention period and for 84 days after the last dose of study intervention, which corresponds to the time needed to eliminate reproductive safety risk of the study intervention:

- Refrain from donating sperm

PLUS either:

- Be abstinent from heterosexual intercourse as their preferred and usual lifestyle (abstinent on a long-term and persistent basis) and agree to remain abstinent.

OR

- Must agree to use a male condom when engaging in any activity that allows for passage of ejaculate to another person.

A male participant should be advised of the benefit for a female of child-bearing potential partner using a highly effective method of contraception with a failure rate of <1% per year.

4. Has provided written informed consent/assent. For underage participants, both the consent of the participant's legal representative or legal guardian and the participant's assent (where applicable) must be obtained based on local requirements.

## 6.2. Exclusion Criteria

Participants meeting any of the following exclusion criteria will not be eligible for study enrollment:

1. Female who is breastfeeding or pregnant.
2. Withdrew consent or was noncompliant from the originating osivelotor clinical study.
3. Has any medical, psychological, safety, or behavioral conditions that, in the opinion of the Investigator, may confound safety interpretation, interfere with compliance, or preclude informed consent.
4. Use of prohibited prescription or nonprescription drugs and dietary supplements (including herbal and alternative medications). Marijuana and all forms of ingested or inhaled cannabidiol (CBD) and THC-containing products usage meeting DSM-V criteria for substance abuse disorder is prohibited. However, occasional marijuana use is allowed, except for 24 hours prior to neurocognitive assessment as outlined in the SoA.
5. Ongoing or recent use of CCI [REDACTED]. Recent is defined as within 5 elimination half-lives or 14 days, whichever is longer prior to Day 1.
6. Ongoing or recent use of CCI [REDACTED]. Recent is defined as within 5 elimination half-lives or 14 days, whichever is longer, prior to Day 1.
7. Ongoing or recent use of the CCI [REDACTED]. Recent is defined as within 5 elimination half-lives prior to Day 1.
8. Current or recent use of voxelotor. Recent use is defined as within 10 days prior to Day 1.
9. Consumption of grapefruit, grapefruit juice, and/or Seville oranges within 14 days prior to Day 1 and is unwilling to abstain from consumption of grapefruit, grapefruit juice, and/or Seville oranges until the EOS/ET.
10. Has received an investigational drug (including investigational vaccines) within 5 times the elimination half-life (if known) or within 30 days (if the elimination half-life is unknown) prior to study drug administration or is concurrently enrolled in any research judged not to be scientifically or medically compatible with this study.
11. Current or recent use of crizanlizumab. Recent use is defined as within 90 days prior to Day 1.

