## 5. STUDY DESIGN

### 5.1. Overall Design

This multicenter, global, open-label extension study is designed to assess the safety of long-term treatment with osivelotor in participants with SCD. The study will be conducted globally and will be available to eligible participants enrolled in a prior Pfizer-sponsored osivelotor clinical study (originating study). Participants must meet the entry criteria for this

study to be eligible for enrollment (see Section 6.1). The study will have a global distribution, and up to approximately 500 participants will be enrolled.

Eligible participants will receive osivelotor administered orally daily if they continue to receive clinical benefit that outweighs risk, as determined by the Investigator, until the participant has access to osivelotor from an alternative source (eg, through commercialization or a managed-access program).

Eligible participants will receive open-label osivelotor at Baseline (Day 1). It is intended that Day 1 coincides with the final visit from the originating osivelotor study. End of Treatment (EOT) assessments from the originating study will serve as Baseline assessments for this study. If Day 1 for this study is greater than 7 days from the completion of the originating study, new baseline assessments will be obtained. If during the period between Day 1 of this study and completion of the originating study no dose is received for greater than 3 consecutive days, an appropriate loading dose will be administered prior to continued maintenance dosing (see Section 11.3 for detail). Additional assessments that may not have been included in the prior EOT assessments are outlined in the Schedule of Assessments and will need to be completed prior to study drug administration.

Participants who participated in Part A of C5351004 or any other open label osivelotor study, will undergo safety and outcome assessments at Baseline (Day 1) and every 12 weeks thereafter (Table 2).

Participants from Part B of C5351004, or any other randomized, blinded, placebo controlled osivelotor study will undergo safety and outcome assessments at Baseline (Day 1), Week 8, Week 16, Week 24, and every 12 weeks thereafter (Table 3).

Pediatric participants from Part C of C5351004 will undergo safety and outcome assessments at Baseline (Day 1), Week 2, Week 4, Week 8, Week 12, Week 16, Week 20, Week 24, and every 12 weeks thereafter (Table 4).

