**Table 14. Modified Loading Dose for Those with a Gap in Treatment from C5351004 Part A, Part B, and Part C**

Amount of Consecutive Days with Missed Doses	100 mg Maintenance Dose	150 mg Maintenance Dose	200 mg Maintenance Dose
>3 to <7 consecutive days of missed doses	200 mg QD x 3 days	300 mg QD x 3 days	300 mg QD x 4 days
7 to <14 consecutive days of missed doses	200 mg QD x 5 days	300 mg QD x 5 days	300 mg QD x 7 days
14 to <42 consecutive days of missed doses	200 mg QD x 7 days	300 mg QD x 7 days	300 mg QD x 10 days
42 consecutive days of missed doses or greater	200 mg QD x 7 days	300 mg QD x 7 days	300 mg QD x 14 days

Abbreviations: BID, twice daily; QD, once daily.

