#### 11.6. Appendix 4: Prohibited and Restricted Concomitant Medications That May Result in DDI

The prohibited concomitant medications listed below (Table 17) should not be taken with osivelotor for the period of time at least equal to the required washout period listed in the table and throughout the conduct of the study. Restricted concomitant medications may be used but with the following restrictions (Table 18).

The Pfizer study team is to be notified of any prohibited or restricted medications taken during the study. After consulting with the sponsor, the investigator will make a judgment on the ongoing participation of any participant with prohibited or restricted medication use during the study.

This list of drugs prohibited and restricted for potential DDI concerns with the IMP may be revised during the course of the study with written notification from the sponsor to include or exclude specific drugs or drug categories for various reasons (eg, emerging DDI results for the IMP, availability of new information in literature on the DDI potential of other drugs) if the overall benefit/risk assessment is not impacted or if the changes do not significantly impact the safety of participants or the scientific value of the trial.

This is not an all-inclusive list. Site staff should consult with the sponsor or designee with any questions regarding potential DDI.

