**Table 17. Examples of Prohibited Concomitant Medications**

Drug Category	Drugs	Washout Period Requirement Prior to First Dose of Osiveltor
CCI		
		5 elimination half-lives or 14 days, whichever is longer
		5 elimination half-lives or 14 days, whichever is longer
Prohibited Juices	Participants are not permitted to consume grapefruit, grapefruit juice, and/or Seville oranges	14 days prior to first dose of osiveltor

Abbreviations: CCI

Note: This is not an exhaustive list. Country-specific lists may be used if available.

For an updated list, refer to the following link: <https://www.fda.gov/drugs/drug-interactions-labeling/drug-development-and-drug-interactions-table-substrates-inhibitors-and-inducers>.

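### Exclusion 9 joins its two grapefruit conditions with *and*, so a recent consumer who agrees to stop can be dosed inside Table 17's 14-day washout

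*Protocol*

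**What the plan says.** Protocol Section 6.2 treats each exclusion as sufficient by itself: "Participants meeting any of the following exclusion criteria will not be eligible for study enrollment". Item 9 is one entry with two parts. The first is "Consumption of grapefruit, grapefruit juice, and/or Seville oranges within 14 days prior to Day 1". The second is refusal to abstain until the EOS or ET visit. They are connected by *and*: "within 14 days prior to Day 1 and is unwilling to abstain from consumption of grapefruit".

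Protocol Section 11.6 governs prohibited substances. Their use alongside study drug is barred "for the period of time at least equal to the required washout period listed in the table and throughout the conduct of the study". Table 17 lists grapefruit and Seville orange products among these substances and sets their washout at "14 days prior to first dose of osiveltor". Neither place makes an exception for a person who promises to stop.

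The neighboring items in Section 6.2 work differently. Items 5 to 8 and 11 each exclude on current or recent use alone; item 8, for example, reads "Current or recent use of voxelotor. Recent use is defined as within 10 days prior to Day 1". Item 10, which also has two parts, joins them with *or*.

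**The concern.** Section 11.6 sets two requirements: a completed washout before dosing, and abstention during the study. An entry criterion meant to protect both should exclude a person who fails either. Item 9 excludes only a person who fails both.

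The important case is the recent consumer who is willing to stop. That person passes item 9, and Section 5.1 intends Day 1 to fall on the final visit of the originating study, so the default timetable allows no time to complete the washout. The site gets two answers: eligible under Section 6.2, not yet ready to dose under Table 17.

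Protocol Section 3.2.1 names drug interactions as a potential risk and relies on monitoring of the prohibited and restricted list to mitigate it. An eligibility rule that admits people inside one of that list's washouts weakens this. Any interaction would fall in the early safety data and in the Day 1 PK samples, which the Schedule of Assessments takes before dosing and 1 to 2 hours after. No estimate, test or sample size depends on the point.

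**Working it through.** The plan states no figure to reproduce. The check is a truth table followed by the cost in days.

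**Eligibility.** Let R be intake in the 14 days before the planned Day 1 (item 9 and Table 17 use the same window) and W be willingness to abstain (item 9). As written, item 9 excludes when R is true and W is false. With *or*, it excludes when R is true or W is false. The washout is unmet on the planned Day 1 whenever R is true.

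| Recent intake (R) | Willing (W) | Item 9 as written | Washout met on planned Day 1? | Item 9 with *or* |
|---|---|---|---|---|
| Yes | No | Excluded | No | Excluded |
| Yes | Yes | **Eligible** | **No** | Excluded until washout is complete |
| No | No | Eligible | Yes; breach only if they later consume | Excluded |
| No | Yes | Eligible | Yes | Eligible |

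- As written: 1 of 4 combinations excluded.
- Washout unmet: 2 of 4. Item 9 stops 1 of those 2.
- No recent intake but unwilling: 1 of 4, admitted with no breach at entry.
- With *or*: 3 of 4 excluded.

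These are counts of logical cases, not of people.

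**Do other exclusions close the gap?** Item 4 covers prohibited drugs and dietary supplements and does not name foods or juices. Item 3 lets the Investigator exclude for behavior that may interfere with compliance. That could reach the unwilling person, but it does not reach a willing recent consumer.

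**Delay needed to complete the washout.** If the last intake was k days before the planned Day 1, the wait is 14 − k days. With k = 1 it is 14 − 1 = 13 days; with k = 13 it is 14 − 13 = 1 day.

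Assume a direct rollover at 150 mg, with daily dosing up to the planned Day 1 and the originating study completed on that day. Section 5.1 then applies: if "no dose is received for greater than 3 consecutive days, an appropriate loading dose will be administered prior to continued maintenance dosing". Table 14 gives the regimen:

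| Wait (days) | k | Loading dose at 150 mg | New baseline (more than 7 days)? |
|---|---|---|---|
| 1 to 3 | 13 to 11 | None | No |
| 4 to 6 | 10 to 8 | 300 mg QD for 3 days | No |
| 7 | 7 | 300 mg QD for 5 days | No |
| 8 to 13 | 6 to 1 | 300 mg QD for 5 days | Yes |

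The last two rows fall in the Table 14 band "7 to <14 consecutive days of missed doses".

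**The case against.** Four points can be made for leaving the text alone.

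1. *Table 17 may not apply at Day 1.* It counts from the first dose of osivelotor. Inclusion 1 requires earlier receipt of study drug, and SAP Section 2.2.3 says that only participants from Part A, which was open label, were enrolled. For them the literal first dose was in the parent study. This does not hold up well. Table 17 belongs to this protocol, and its washout of five half-lives or 14 days, whichever is longer, is the same period that items 5 and 6 count back from this study's Day 1. Item 9 also counts from Day 1. Drug names are redacted, so rows and items cannot be matched one to one, but the shared form supports reading the first dose as the first in this study.

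2. *Section 11.6 already prevents the breach.* This stands in part. Passing item 9 does not waive the washout, and a site following the whole protocol would delay Day 1. The defect is a disagreement between the entry rule and the washout rule; the washout rule itself is not missing.

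3. *The* and *may be deliberate.* In a rollover study, a sponsor might accept a willing recent consumer to avoid interrupting treatment. The protocol does not say so, and if that is the intention Table 17 needs the exception.

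4. *Little is at stake.* This stands. The number of consumers and the effect of grapefruit are not given, direct rollovers from Part A already have osivelotor exposure, and the SAP describes enrollment in the past tense. It limits the importance of the point, not its correctness.

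**Conclusion.** The concern holds. Item 9 as worded does not enforce the washout and abstention that Section 11.6 and Table 17 require: it stops one of the two combinations that would break the washout on the planned Day 1, and it also admits a person who has declined to keep the on-study ban. The conclusion rests on the plain reading of *and*, and on taking Table 17's first dose to be the first dose in this study. Confidence in the inconsistency is high. Its importance is low: it does not touch the analysis, its clinical size cannot be judged from the documents, and it may now affect few or no enrollment decisions.

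**What to change.** In item 9 replace *and* with *or* before the unwillingness clause. Alternatively, split it into two criteria: (a) intake in the 14 days before Day 1, and (b) unwillingness to abstain until EOS/ET. Entry then agrees with Section 11.6 and Table 17, and a willing recent consumer can still join once Day 1 is moved to complete the 14 days. If the sponsor does want such people to start without delay, Table 17 should state that exception instead.

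The edit is one word, but changing an eligibility criterion is a protocol amendment that needs IRB/IEC approval before use (Section 11.1.1). For a willing recent consumer the cost is the 1 to 13 day wait, with reloading and new baseline assessments where the gap triggers them. Table 17 already implies that wait, and Section 5.1 and Table 14 already provide for its consequences.

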## 7. STUDY TREATMENT AND CONCOMITANT THERAPY

### 7.1. Study Treatments Administered

Study drug information is presented below.

**Table 7. Study Drug Information**

Study Intervention	
Intervention Name	Osivelotor (PF-07940367 or GBT021601)
Type	Drug
Use	Experimental
IMP or NIMP/AxMP	IMP
Dose Formulation	Tablet (or age appropriate oral formulation for pediatric participants <6 years of age)
Unit Dose Strength(s)	100 mg/tablet, 25 mg/tablet
Dosage Level(s)	100 mg, 150 mg, 200 mg
Route of Administration	oral
Sourcing	Provided centrally by the sponsor.
Packaging and Labeling	Study intervention will be provided in bottles. Each bottle will be labeled as required per country requirement. Provided blinded.
SRSD	PF-07940367 Investigator's Brochure
Study Arms	
Arm Title	Osivelotor (PF-07940367 or GBT021601)
Adults	Adult participants enrolling from C5351004 Part A and Part B will receive 150 mg maintenance dose. Dose adjustment and/or loading dose will be determined based on previous intervention/dose received in C5351004. Details are provided in Appendix 1.
Adolescents and Pediatrics	Adolescent and pediatric participants from C5351004 Parts B and C will be administered a dose that provides generally equivalent exposure to adult participants.

See [Appendix 1: Detailed Dosing Information For Osivelotor](#) for dose information for participants rolling into this study.

Osivelotor will be administered orally. Study drug will be dispensed to the participant for completion of loading doses and initiation of maintenance dosing at home daily until the next clinical site visit.

Study drug should be taken two hours before a meal or one hour after a meal. Each dose will be administered orally with approximately 240 mL of water (additional water to complete dosing is allowed). Participants should swallow the tablets ( $\geq 6$  years old) or age appropriate

pediatric formulation (<6 years old) within 5 minutes. If the participant vomits, the dose should not be repeated.

On the days that PK samples are to be taken, study drug is to be taken in the clinic and the participant must record the time and date of the last three doses of study drug taken at home. It is anticipated that these samples are to be taken  $24 \pm 3$  hours after the last dose at home.

## **7.2. Preparation, Handling, Storage, and Accountability**

Osivelotor will be provided in high density polyethylene bottles with child resistant caps with induction seal and labeled according to local regulations.

Study drug will be stored at controlled room temperature between 15°C to 25°C, either in the storage area of the investigational site pharmacy, which is a secure, temperature controlled, locked environment with restricted access, or in a secure location at the participants' home.

No special considerations for safe handling of osivelotor are required.

The Investigator or designee must confirm appropriate temperature conditions have been maintained during transit for all study drug received, and any discrepancies are reported and resolved before use of the study intervention.

Only participants enrolled in the study may receive study intervention, and only authorized site staff may supply or administer study intervention.

The Investigator, institution, or the head of the medical institution (where applicable) is responsible for study intervention accountability, reconciliation, and record maintenance (ie, receipt, reconciliation, and final disposition records).

Further guidance and information for the final disposition of unused study interventions are provided in the Study Reference Manual or Pharmacy Manual.

## **7.3. Randomization and Blinding**

This is an open-label study. Randomization and blinding are not applicable.

As this is an open-label, long-term extension study, the sponsor may conduct unblinded reviews and/or summaries of the data during the course of the study for the purpose of safety assessment, supporting clinical development, and/or supporting regulatory review.

## **7.4. Study Treatment Compliance**

The first dose of the study drug will be administered by clinical staff at the study site. Details regarding dosing, including the dose administered and the date and time of dosing, will be recorded. The participant/parent/legal guardian/legally authorized representative will be required to bring the dispensed osivelotor bottle(s) to the study center at each visit and the Investigator or designee is to confirm the number of tablets or amount of age-appropriate formulation taken and remaining before the next dispensation.

The participant/parent/legal guardian/legally authorized representative will also be supplied with a diary on which to record the date and time each dose of study drug is taken. Reasons for missed doses should be recorded. The diary will be dispensed at onsite visits and the participant will be required to bring the diary to each visit at the study center where the

Investigator or designee will review the records and enter the details into the electronic case report form (eCRF).

If a participant misses a dose, the participants should resume normal dosing the next day (ie, the dose on the day after a missed dose should not be increased or decreased).

